3.1 Study Design

This research is a natural experiment study of the impact of introducing MUP in Scotland. The methods involve a repeated cross-sectional audit of all alcohol-related attendances at EDs in two Scottish hospitals and two North England geographical control hospitals at three time points. On each occasion, data collection will involve a face-to-face survey administered by research nurses to ED patients over selected times during a three week time period. All study documents with the exception of the patient information sheet and consent form will be

electronic and held on an iPad. Back up paper copies will be available in case of iPad failure. The study methods and tools are based on previous studies that have been used to quantify the national prevalence of alcohol-related attendances in Emergency Departments in England [36] and by the experience of the Scottish Emergency Department Alcohol Audit, carried out across 15-20 hospitals throughout mainland Scotland between October 2005 and June 2007 [37]. Prior to formal data collection, the processes for collecting data will be piloted – initially within Glasgow only, followed by pilot data collection at all four sites.

The study has been designed to be robust to potential delays in the timing of the intervention. Since the implementation of MUP is not under the control of the investigators, it is possible that there may be delays in the timing of the intervention. Baseline data collection will occur as soon as is practically possible. The 2nd and 3rd waves of data collection will take place six and 12 months post implementation. If implementation of MUP occurs more than 12 months after baseline the 2nd wave will be conducted shortly before implementation to act as a 2nd baseline. The 3rd wave will remain as close to a 12 month follow-up as feasible. If this occurs, it will not be possible to investigate whether the intervention effect varies over time (RO5). In general, investigators will attempt to avoid conducting data collection during months that are expected to be atypical in terms of alcohol consumption (i.e. Dec-Jan and Jun-Aug). Furthermore, we will attempt to collect data for one follow-up wave at the same time of year as the baseline data, to control for seasonal variation in consumption.

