Based on the experience of the 24 hour audit of Emergency Departments in England, we have assumed that we will be able to recruit at least 50% of eligible ED attendees. We anticipate that the four sites will result in 940 recruits per week. Recruiting over three weeks pre- and post-intervention – giving a total sample size of 5640 – would mean that we would be highly powered (>80%) to detect a decrease in the proportion of alcohol-related attendances from 30% to 25% with 95% significance. We have used a base rate of 30% informed by the 24 hour audit of EDs in England and assumed a 5% decrease would be of public health importance and may be expected based on current evidence. For subgroup analyses, we would have good power (>80%) to detect an effect size of 0.23 on the FAST score among those from the most deprived quintile (estimated to be 25% of attendances) and an effect size of 0.27 among those aged 18-24 (estimated to be 15% of attendances. Two separate follow-up times are required to determine if intervention effects vary over time.

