3.7 Data Collection

Each wave will collect data over three weeks, ideally with one wave of data collection prior to the implementation of MUP and two post-implementation waves (after six months and 12 months). To maximise collection of both alcohol-related attendances and hazardous drinkers, data collection will occur from 2000 to 0400 on Thursday to Sunday (i.e. 32 hours per week during this time period) and 0900-1700 on Monday to Wednesday (i.e. 24 hours per week during this time period). If deemed necessary by local sites, different 8 hour timeslots will be considered, to meet local attendance patterns. As noted above, periods of the year when alcohol consumption is atypical will be avoided.

Patients will be approached by research staff to seek permission to complete a short face-to-face interview. The reasons for exclusion will be recorded electronically on the iPad along with 5 year age group and sex. Excluded patients will not be assigned a study ID and so will be completely anonymous.

All suitable patients will be approached, their eligibility confirmed, and, if eligible, informed consent will be sought and a face-to-face interview administered, based on a previously used patient questionnaire [36]. Research nurses will be responsible for obtaining written informed consent, completing the data linkage form if consent has been obtained -and then proceeding to conduct the face-to-face survey. These will all be electronic documents contained on an iPAD.

The face-to-face survey will collect information on socio-demographic details, problematic alcohol use (FAST Alcohol Screening Test), alcohol consumption in the last 24 hours, self-assessment of whether alcohol contributed to the attendance and self-report of whether the patient has been a victim of violence. Research nurses will input the information into the standardised electronic form which will include a number of options to assist with timely completion. Paper versions of the survey, and consent and linkage forms are enclosed (ED Survey v2.5). The Interview Schedule for Pilot Phase v2.5 and Qualitative Interview for Pilot Phase will be on paper only. Back up paper copies of all electronic documents will be available in case of iPad failure. An ED attendance database will be maintained for all attendances during data collection periods to allow monitoring of patient recruitment.

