Research staff will retrieve additional data on participants from patient records, either during data collection sessions (if time allows), or at a later time. The following information will be sought from the clinical records:

- demographic characteristics (date of birth, sex, postcode),
- attendance details (time, triage category),
- discharge status
- diagnoses at discharge (coded by ICD10 categories) and all relevant data relating to reason for admission and diagnosis (whether ICD10 or another coding system or free text).

We will calculate the consent rate among those eligible. However we need to assess the representativeness of the interviewees and attendees in the study timeslots, and the certainty of our estimates of the proportion of attendances that are alcohol-related. To make this possible, we propose to request from hospital records anonymised information on all attendees over the three week data collection periods for each wave. We wish to ask for 5 year age groups, sex, reason for attendance, and other relevant data for diagnosis (whether ICD10 or another coding system or free text). We will request that attendees within the timeslots for the study are flagged, so that we can calculate a true recruitment rate for those interviewed and for whom we have reasons for exclusion.

Data collection will be conducted by Clinical Research Facilities (CRFs), on behalf of the study team. Each CRF will be responsible for ensuring line management of their staff, as per their usual operating procedures. The research nurses responsible for data collection will have received training, with training available for additional research nurses (to allow for rota gaps to be filled, in the event of illness etc.). It is recommended that any data collection session should include at least one more experienced research nurse, so that more junior research nurses feel adequately supported. Research nurses will be able to contact a member of the study team throughout data collection periods in the event of an emergency.

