3.8 Data Analysis

Primary outcome

The primary outcome will be changes in absolute numbers of alcohol-related attendances as defined by any one of:

- patient self-reports attendance is alcohol-related
- patient reports alcohol consumption in past 24 hours of ≥8units in men or ≥6 units in women
- patient not approached because too intoxicated with alcohol

Secondary outcomes

Secondary outcomes will be changes in:

- absolute number of alcohol-related attendances by age/sex/deprivation
- problematic alcohol use (as defined by the Fast Alcohol Screening Test (FAST))
- mean FAST score
- prevalence of binge drinking in the past week
- reason for attendance (coded by ICD10)

After the first post-intervention wave, we will test for differences in the outcomes between the intervention and comparison groups using a fixed-effects regression model, with individuals nested within EDs, before and after adjustment for relevant covariates including baseline levels of alcohol-related attendance, demography, triage category etc. We will also attempt to determine the nature of the effect more precisely in terms of whether a dose-response effect according to the time since MUP was implemented (through a test of the significance of an interaction between time and intervention). We will test for interactions of the intervention with defined important covariates (including age, gender, deprivation quintile, disease diagnostic categories) to investigate the possibility of differential intervention effects and will subsequently stratify the analyses if indicated.

4. Research Governance and Regulatory Issues

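### Triage category is named as an adjustment covariate although it is set at the counted attendance, so the adjusted MUP estimate can be distorted if MUP shifts triage

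*Protocol*

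**What the plan says.** Protocol section 3.8 (Data Analysis) tests for differences between the intervention and comparison groups with a fixed-effects regression, individuals nested within EDs, "before and after adjustment for relevant covariates including baseline levels of alcohol-related attendance, demography, triage category etc". It gives no reason for including triage, no link function, and no statement of which estimate is the main result.

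Section 3.7 (Data Collection) lists what is taken from participants' clinical records, including "attendance details (time, triage category" as details of the attendance. The outcome in section 3.8 classifies that same attendance. Besides self-attribution, its criteria are "patient reports alcohol consumption in past 24 hours of ≥8units in men or ≥6 units in women" and "patient not approached because too intoxicated with alcohol".

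On design, section 3.1 states: "The methods involve a repeated cross-sectional audit of all alcohol-related attendances at EDs in two Scottish hospitals and two North England geographical control hospitals". Each wave is therefore a new sample of attendances.

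**The concern.** A covariate removes confounding when it is fixed before the exposure can act. Age, sex and area deprivation are characteristics a person brings to the ED. Triage category is not: staff assign it at the attendance, after the drinking has taken place and, in the post-implementation waves, after MUP has begun. Because the samples are repeated cross-sections, no one seen after MUP has a pre-MUP triage value that could stand in for it.

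If MUP makes alcohol-related attendances less severe, or changes how they are triaged, triage is in part a consequence of both the exposure and the outcome. Holding it fixed then compares groups that are no longer alike. At stake is the adjusted answer to research objective 1. In a non-randomised study that acknowledges confounding (section 3.1), many readers will look to the adjusted figure first.

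**Working it through.** **Inputs from the documents.** Section 3.3 powers the study to "detect a decrease in the proportion of alcohol-related attendances from 30% to 25% with 95% significance", with 5640 recruits over one pre- and one post-implementation wave, i.e. 2820 per wave. With equal recruitment by site that is 1410 per country per wave. No triage distribution is given, so every triage figure below is an assumption. England is held at 30% throughout, so the Scottish pre-post change equals the difference-in-differences.

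**Step 1: the plan's own figure.** The only stated figure is power above 80%. Two-sided 5% test with pooled variance: power = Φ[(0.05√n − 1.96√(2 × 0.275 × 0.725)) / √(0.30 × 0.70 + 0.25 × 0.75)].
- n = 2820 per group: (2.655 − 1.238)/0.630 = 2.25, power 98.8%.
- n = 1410 per group: (1.878 − 1.238)/0.630 = 1.01, power 84.5%.

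The claim is reproduced for a simple two-group comparison. Whether that is the right comparison is outside this point. The present issue does not change it.

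**Step 2: triage shifts, nothing is prevented.** Assume, per 100 attendances before MUP, 40 urgent (20 alcohol-related) and 60 other (10 alcohol-related). After MUP, 5 of the 20 urgent alcohol-related cases are triaged lower.

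| | Before | After |
|---|---|---|
| Urgent | 20/40 | 15/35 |
| Other | 10/60 | 15/65 |
| All | 30/100 | 30/100 |

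The crude change is 0.0 points. Mantel-Haenszel risk difference:
- Urgent: (15×40 − 20×35)/75 = −1.333; weight 35×40/75 = 18.667.
- Other: (15×60 − 10×65)/125 = +2.000; weight 65×60/125 = 31.200.
- Adjusted: 0.667/49.867 = **+1.3 points**.

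Mantel-Haenszel odds ratio: (15×20/75 + 15×50/125)/(20×20/75 + 50×10/125) = 10.000/9.333 = **1.07**.

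**Step 3: the four-cell regression.** Country by period, 1410 per cell, expected counts, fitted with and without a binary triage term. The urgent share is 25% among other attendances throughout. Without triage, the true effect is recovered in every row.

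| Urgent share among alcohol-related attendances | True change (points) | Triage-adjusted change | Triage-adjusted OR (unadjusted) |
|---|---|---|---|
| 35% to 65%, same before and after MUP | −5.0 | −4.95 to −4.29 | 0.778 (0.778) |
| 45%, falling to 35% with MUP | −5.0 | −4.40 | 0.796 (0.778) |
| 55%, falling to 45% | −5.0 | −3.97 | 0.806 (0.778) |
| 55%, falling to 35% | −5.0 | −3.45 | 0.831 (0.778) |
| 45%, falling to 35% | 0 | +0.5 | 1.03 (1.00) |
| 55%, falling to 45% | 0 | +0.8 | 1.04 (1.00) |
| 55%, falling to 35% | 0 | +1.4 | 1.08 (1.00) |

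The first row has an exact explanation on the odds scale. If the chance of each triage level given alcohol status is the same in all four cells, stratifying multiplies every cell's odds by the same factor. The odds ratio stays at (0.25/0.75)/(0.30/0.70) = 0.778. On the linear scale 1% to 14% is lost. Once MUP also shifts triage, 12% to 31% of the risk difference is lost and the odds ratio moves too.

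**The case against.** Several points on the other side stand.

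- **An unaffected estimate is planned.** Results are to be given before and after adjustment, so nothing is lost from the unadjusted answer. A reader might infer that the study's main result is compromised; the protocol does not support that, because it never makes the triage-adjusted estimate primary.
- **The scale matters.** With triage dependent on alcohol status alone, a logistic model shows no distortion. The primary outcome is worded as absolute numbers. In a log-linear model of counts by triage stratum, Step 2 gives (15 + 15)/(20 + 10) = 1.00, with no false effect. The concern needs a model of proportions, which the reference to individuals nested within EDs makes plausible but does not state.
- **Prevention alone does not single out triage.** It is tempting to argue that if MUP prevents urgent cases, adjustment strips out the benefit. With the Step 2 baseline and 6.67 urgent alcohol-related cases prevented, the strata become 13.33/33.33 and 10/60: the crude change is −5.0 points and the adjusted change −1.818/48.18 = −3.8. Preventing 22% evenly in both strata gives −4.4, with the odds ratio still 0.778. Relabel the strata as male and female, or by deprivation, and the same figures appear for covariates that should stay. Only a MUP-induced shift in triage sets triage apart.
- **That shift is assumed.** Nothing in the protocol says that MUP or intoxication changes triage; it is reasoned from timing and the outcome definition.
- **Triage may carry case-mix information.** Patients too unwell, or admitted, are excluded (section 3.3), so dropping triage may give up a little control.

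The covariate list is open-ended and an analysis plan may refine it. That does not dispose of the point, because triage is one of the few covariates the protocol names.

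One further inference should be set aside. Excluded patients have only reason, age group and sex recorded, and "Excluded patients will not be assigned a study ID and so will be completely anonymous", so those too intoxicated to approach have no triage value. But they have no postcode-based deprivation either. That is a separate data-availability question, not an argument against triage in particular.

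**Conclusion.** The point holds in a limited form. The protocol names as a covariate something determined at the outcome-defining attendance, after MUP and after the drinking, and offers no ground for treating it as a confounder. In a model of proportions the adjusted estimate is then open to attenuation or a false effect, provided MUP changes the severity or triage of alcohol-related attendances.

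Under the assumed distributions, a true fall of 5.0 points appears as 3.45 to 4.4 points, and a null effect appears as +0.5 to +1.4 points (odds ratio 1.03 to 1.08). The protocol itself treats a 5-point fall as important, so distortions of this order would matter for interpretation, but they are illustrations and not estimates. Larger distortions require the triage shift to extend to all Scottish attendances, for which the documents give still less reason. The calculations cover the primary outcome only. A reader might infer that adjusting for triage always biases the result; the first row of the Step 3 table shows that it does not on the odds-ratio scale.

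**What to change.** In section 3.8, remove triage category from the main adjustment set. Keep ED, wave and characteristics fixed before attendance (age, sex, area deprivation). State whether the unadjusted or the adjusted estimate is the main result. If triage is used at all, confine it to a sensitivity analysis labelled as conditioning on a variable set at the attendance, or report it descriptively.

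The cost is a line or two of wording and no new data. The downside is a small possible loss of precision, if triage predicts the outcome, and of case-mix control; the sensitivity analysis would show how much that matters.

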2.3 Aims/Objectives/Research questions

The overarching NIHR grant includes three related studies that together make an important contribution to the overarching evaluation of the impact of MUP in Scotland. The three research

aims and their associated studies are summarised in the Table below. The remainder of this protocol will only focus on the Emergency Department (ED) study, with a separate protocol available for the survey of alcohol-related behaviours (which involves data collection within sexual health clinics).

Research aims (RAs)	Study components
RA1: To determine the impact on alcohol-related harms	Emergency Department study;
and drinking patterns for the overall population and by	Survey of alcohol-related
subgroups of interest (age, sex and deprivation)	behaviours (C1)
RA2: To determine the impact on non-alcohol substance	Survey of alcohol-related
use for the overall population and by subgroups of interest	behaviours(C2); Qualitative focus
(age, sex and deprivation).	group study (C3)
RA3: To describe changes in experiences and norms	Qualitative focus group study (C3)
towards MUP and alcohol use following the introduction of	
MUP by subgroups of interest (age, sex and deprivation).	

The more specific research objectives (ROs) of the ED study are as follows:

- 1. To determine the impact of MUP on alcohol-related ED attendances amongst the general population
- 2. To determine whether the effect of MUP differs across the following population subgroups
 - a. Age group
 - b. Gender
 - c. Area-based deprivation
- 3. To determine whether the effect of MUP varies dependent on the type of alcohol-related harm:
 - a. Acute alcohol-related harms vs chronic alcohol-related harms
 - b. Broad diagnostic groups (on the basis of ICD categories)
- 4. To investigate whether alcohol consumption (on the basis of the FAST score: sensible, hazardous, harmful, possible dependence) has changed amongst people attending EDs over time
- 5. To investigate whether the intervention effect size varies over time

3 Study Design/Methods

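### RO3 treats diagnosis as an effect modifier, although diagnosis describes the attendance being counted; fitted to a yes/no outcome per attender, an almost wholly alcohol-related group would show little or nothing

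*Protocol*

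**What the plan says.** Protocol section 2.3 sets RO3: "To determine whether the effect of MUP varies dependent on the type of alcohol-related harm". It names two splits, acute against chronic harm and "Broad diagnostic groups (on the basis of ICD categories".

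Section 3.8 then states:
- Primary outcome scale: "The primary outcome will be changes in absolute numbers of alcohol-related attendances as defined by any one of" three criteria (self-report, units in 24 hours, intoxication). One of them is "patient not approached because too intoxicated with alcohol".
- Model: a comparison of intervention and control groups "using a fixed-effects regression model, with individuals nested within EDs".
- Differential effects: "We will test for interactions of the intervention with defined important covariates (including age, gender, deprivation quintile, disease diagnostic categories", with stratified analyses afterwards if indicated.
- Secondary outcomes: these include "reason for attendance (coded by ICD10" for attendances in general. The breakdown of alcohol-related numbers is by age, sex and deprivation; diagnosis is not in it.

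Section 3.7 says that records will supply "diagnoses at discharge (coded by ICD10 categories". It also says that excluded patients get no study ID, and that only the reason for exclusion, five-year age group and sex are recorded for them.

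The power statement in section 3.3 is on a proportion, 30% against 25%.

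**The concern.** Age, sex and deprivation are settled before the patient attends. Diagnosis is not: it is part of the harm that RO3 asks about, and the same section lets MUP change it. One variable is therefore both outcome and effect modifier.

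This matters if the model has one yes/no record per attender, which nesting individuals within EDs suggests. Each diagnostic group is then compared on the share of its own attenders who are alcohol-related. In a group that is nearly all alcohol-related, a prevented attendance leaves numerator and denominator together, and the share hardly moves. The groups most specific to alcohol could then yield no usable estimate. RO3 has its own planned papers (section 7), and the study's findings go to the Scottish Government's report to Parliament (section 6.3).

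**Working it through.** **Stated figures.** 235 per week per site × 3 weeks × 4 sites = 2820 per wave; × 2 = 5640. With 2820 per group, 30% against 25% and two-sided 5%, power is 98.8%, which agrees with the stated figure of over 80%. No stated figure bears on RO3 itself, so the rest uses assumed cases.

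**Step 1: the design effect placed in one diagnostic group.** Assume equal recruitment, so 2820 / 2 = 1410 Scottish attenders per wave, of whom 30% = 423 are alcohol-related. Let x alcohol-related attendances be prevented and nothing else change:

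(423 − x) / (1410 − x) = 0.25, so x = 70.5 / 0.75 = 94, and 329 / 1316 = 25.0%.

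Let all 94 come from a wholly alcohol-caused group. The protocol does not give the size of such a group; take 7% to 20% of attendances, all meeting the outcome.

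| Share of attendances | Number before → after | Fall in number | Share alcohol-related in group | Share alcohol-related in the rest |
|---|---|---|---|---|
| 7% | 98.7 → 4.7 | 95% | 100% → 100% | 24.7% → 24.7% |
| 10% | 141 → 47 | 67% | 100% → 100% | 22.2% → 22.2% |
| 15% | 211.5 → 117.5 | 44% | 100% → 100% | 17.6% → 17.6% |
| 20% | 282 → 188 | 33% | 100% → 100% | 12.5% → 12.5% |

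The full design effect has occurred, yet no within-group share moves. At 100% the group's odds ratio cannot be estimated.

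**Step 2: a group just below 100%.** Take 60 attendances, 59 meeting the outcome, and a true fall of 30%.
- If the non-qualifying case falls in proportion: 59/60 = 98.3% and 41.3/42 = 98.3%, so the odds ratio is 1.00.
- If the non-qualifying case is unaffected: odds go from 59/1 to 41.3/1, so the odds ratio is 0.70, the true ratio. But SE(log OR) = √(1/59 + 1/1 + 1/41.3 + 1/1) = 1.43, giving a 95% interval of 0.04 to 11.5. The ratio of numbers, 41.3/59 = 0.70, has SE(log) = √(1/59 + 1/41.3) = 0.20 and an interval of 0.47 to 1.04.

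**Step 3: mixed groups.** Assume 300 injuries, 90 alcohol-related, a 30% fall in those 90 and no change in the other 210. The share goes from 30.0% to 63/273 = 23.1%, a ratio of 0.77. The odds ratio is (63/210) / (90/210) = 0.70, equal to the ratio of numbers. The same holds if a group is halved by preventing only qualifying cases:
- 80% → 60%: odds ratio (30/20) / (80/20) = 0.375; numbers 30/80 = 0.375.
- 95% → 90%: odds ratio (45/5) / (95/5) = 0.474; numbers 45/95 = 0.474.

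**Step 4: both models on the same expected counts.** Assume 1410 attenders per country and wave, 30% alcohol-related overall, and a group with 10% of attendances of which 98% (or 90%) qualify. It halves in Scotland after MUP, qualifying or not; nothing else changes.
- Logistic model per attender: effect odds ratio 1.00 within each diagnostic group and interaction odds ratio 1.00. Once diagnosis is in the model, the overall odds ratio moves from 0.84 (0.86) to 1.00.
- Poisson model on alcohol-related numbers by diagnosis: ratio of rate ratios 0.50. At 98%, SE(log) = √(3/138.18 + 1/69.09 + 4/284.82) = 0.224, z = 0.693 / 0.224 = 3.09, p = 0.002; at 90%, p = 0.003. No overdispersion or ED clustering is allowed for.

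**Step 5: ICD-10 reason for attendance as an outcome.** In the 10% row of step 1, the group's share of all attendances falls from 10% to 47/1316 = 3.6%. The change in case mix is visible, without separating alcohol-related attendances within a mixed group.

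**The case against.** The strongest reply is that the primary outcome is worded as absolute numbers. On that scale an intervention-by-diagnosis comparison contrasts diagnosis-specific falls, which is what RO3 asks, and step 4 shows that it works. This stands: the protocol does not say whether the interaction is fitted to numbers or to a yes/no outcome. Individual-level wording and power on a proportion point to the latter, and the listed breakdown of numbers omits diagnosis, but none of this settles it.

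Three stronger readings are tempting and should not be drawn:
- That the interaction is the only route to RO3. ICD-10 reason for attendance is a listed outcome and gives a second, partial route.
- That a fall in alcohol-caused attendances will show as no effect. The exact null needs a yes/no model, and either a group at 100% or non-qualifying cases that fall in proportion. The outcome rests on self-report, recent units or intoxication, so a chronic alcohol diagnosis need not be near 100%. RO3 also speaks of broad ICD groups, not of a wholly alcohol-caused one.
- That effects in mixed groups such as injury are understated. On the odds-ratio scale they are not, if non-alcohol attendances are unchanged (step 3).

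One may add that model detail belongs in a statistical analysis plan, which is not at hand. That covers the choice of scale. It does not cover listing diagnosis as a covariate of the same kind as age and gender, which the protocol itself does.

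**Conclusion.** The point holds as a conditional one. Section 3.8 places a feature of the counted attendance among the effect modifiers of an individual-level regression. Under a yes/no outcome, a diagnostic group that is almost wholly alcohol-related then gives an effect that is null, inestimable or very imprecise: in the assumed 10% case, a 67% fall in numbers with no change in any within-group share. Mixed groups are attenuated on the proportion scale only. On absolute numbers by diagnosis the fall is visible.

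The sizes rest on assumed group shares, equal recruitment by country, unchanged English attendances and no clustering. The issue concerns a secondary objective; the primary comparison is not shown to be wrong. It is still more than missing detail, because a better specification is available from data already planned.

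**What to change.** In section 3.8 and the analysis plan:
- Remove diagnostic category from the covariates for interaction tests and from the strata that follow.
- State that RO3 is answered with type-specific outcomes: the number of alcohol-related attendances in each broad diagnostic group, and in acute and chronic harm, by country and period. Use Poisson or negative binomial models, or a common all-attender denominator, and compare the Scotland-by-post effects across types.
- Count patients not approached because of alcohol intoxication as an acute category of their own. They enter the primary outcome but have no study ID and no individually linked diagnosis, so they cannot be put in an ICD group.

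The cost is wording; no new data are needed. The drawback is small cells. For a Scotland-by-post effect on numbers within one group, with 1410 attenders per country and wave, all of the group qualifying and no overdispersion, power to detect a 25% fall is about 21%, 37% and 64% for groups of 5%, 10% and 20% of attendances. For a halving it is about 74%, 96% and over 99%. Fewer, broader groups may be needed, and are best fixed before the follow-up data are seen.
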